3.1.3 Overall visit response – site investigator data

Table 5 defines how the previously defined TL and NTL visit responses will be combined with new lesion information to give an overall visit response.

Table 5 Overall visit responses

TARGET	NON-TARGET	NEW LESIONS	OVERALL VISIT RESPONSE
CR	CR or NA	No (or NE)	CR
CR	Non-CR/Non-PD or NE	No (or NE)	PR
PR	Non-PD or NE or NA	No (or NE)	PR
SD	Non-PD or NE or NA	No (or NE)	SD
PD	Any	Any	PD
Any	PD	Any	PD
Any	Any	Yes	PD
NE	Non-PD or NE or NA	No (or NE)	NE
NA	CR	No (or NE)	CR
NA	Non-CR/Non-PD	No (or NE)	SD
NA	NE	No (or NE)	NE
NA	NA	No (or NE)	NED

3.1.4 Independent review

A planned blinded independent central review (BICR) of all radiological imaging data will be carried out using RECIST version 1.1. All radiological scans for all patients (including those at unscheduled visits, or outside visit windows) will be collected on an ongoing basis and sent to an AstraZeneca appointed Contract Research Organisation (CRO) for central analysis. The imaging scans will be reviewed by two independent radiologists using RECIST 1.1 and will be adjudicated, if required (i.e. two reviewers' review the scans and adjudication is performed by a separate reviewer in case of a disagreement). For each patient, the BICR will define the overall visit response (i.e. the response obtained overall at each visit by assessing TLs, NTLs and new lesions) data and no programmatic derivation of visit response is necessary. (For patients with TLs at baseline: CR, PR, SD, PD, NE; for patients with NTLs only: CR, SD, PD, NE; for patients with no disease identified at baseline: PD, no evidence of disease [NED], NE). If a patient has had a tumour assessment that cannot be evaluated then the patient will be assigned a visit response of NE (unless there is evidence of progression in which case the response will be assigned as PD). RECIST assessments/scans contributing towards a particular visit may be performed on different dates and for the central review the date of progression for each reviewer will be provided based on the earliest of the scan dates of the component that triggered the progression.

If adjudication is performed, the reviewer that the adjudicator agreed with will be selected as a single reviewer (note in the case of more than one review period, the latest adjudicator decision will be used). In the absence of adjudication, the records for all visits for a single reviewer will be used. The reviewer selected in the absence of adjudication will be the reviewer who read the baseline scan first. The records from the single selected reviewer will be used to report all BICR RECIST information including dates of progression, visit response, censoring and changes in target lesion dimensions. Endpoints (of ORR, PFS and duration of response [DoR]) will be derived programmatically from this information.

Results of this independent review will not be communicated to investigators and the management of patients will be based solely upon the results of the RECIST 1.1 assessment conducted by the investigator.

A BICR of all patients will be performed for the final database lock, which will cover all of the scans up to the data cut-off (DCO).

Further details of the BICR will be documented in the BICR Charter.

3.2 Efficacy Variables

3.2.1 Objective response rate (ORR)

ORR is defined as the percentage of patients with at least one investigator-assessed visit response of CR or PR and will be based on a subset of all randomised patients with measurable disease at baseline per the site investigator. ORR will also be defined using the BICR data to

define a visit response of CR or PR, with the denominator defined as subset of all randomised patients with measurable disease at baseline per BICR.

Data obtained up until progression, or last evaluable assessment in the absence of progression, will be included in the assessment of ORR. Patients who discontinue randomised treatment without progression, receive a subsequent anti-cancer therapy (note that for this analysis radiotherapy is not considered a subsequent anti-cancer therapy) and then respond will not be included as responders in the ORR.

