Under CSP V3.0, as a result of AstraZeneca's decision to terminate study recruitment early, the planned interim futility analysis and primary analysis will not be performed, and there will be no requirement for data review by the IDMC. Alternatively, an initial data cut-off (DCO) will occur following the early termination of study recruitment to allow an early review of the data by AstraZeneca. The study will be unblinded after completion of data cleaning activities on the initial DCO data, and patients on savolitinib monotherapy (savolitinib plus placebo) will be given the opportunity to cross-over to the savolitinib plus osimertinib arm after approval by AstraZeneca.

If it is decided that a patient will switch to savolitinib plus osimertinib before final database lock, then they will follow the scheduled procedures described in CSP Table 2. Patients may otherwise choose to remain on savolitinib monotherapy (as long as, in the opinion of the investigator, they are still receiving clinical benefit and have not reported PD). All patients will be followed until the final DCO for the final analysis, which will occur after all randomised patients have had a 9-month follow-up. CCI

For an overview of the study design see [Figure 1](#).

Figure 1 Study Design

EGFRm+ = Epidermal growth factor receptor mutation positive; MET = Hepatocyte growth factor receptor; NSCLC = Non-small cell lung cancer.

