2 ANALYSIS SETS

2.1 Definition of Analysis Sets

Patients will be assigned to the following analysis sets prior to any analyses being performed.

Full Analysis Set (FAS)

The FAS will include all randomised patients with treatment groups assigned in accordance with the randomisation, regardless of the treatment actually received. Patients who were randomised but did not subsequently receive treatment are included in the FAS. The analysis of data using the FAS therefore follows the principles of intention to treat.

The FAS will be the primary population for reporting efficacy data and to summarise baseline characteristics.

Safety analysis set (SAF)

The Safety analysis set will consist of all randomised patients who received any amount of study treatment. Safety data will not be formally analysed but summarised using the safety analysis set according to the treatment received. If a patient receives any amount of an experimental therapy, they will be summarised in the treatment group corresponding to the first experimental treatment they received.

Cross-over analysis set

The Cross-over analysis set will consist of all patients who were randomised to savolitinib in combination with placebo and received at least one dose of savolitinib plus osimertinib in the cross-over period of the study.

It will be used as the population for reporting the efficacy and safety data for patients who crossed over to treatment with savolitinib plus osimertinib following objective progression on savolitinib plus placebo.

PK analysis set

All patients who receive at least one dose of savolitinib or osimertinib as per the protocol, for whom there are at least one reportable PK concentration without any protocol deviation impacting PK, will be included in the PK analysis set. If a patient receives any amount of an experimental therapy, they will be summarised in the treatment group corresponding to the first experimental treatment they received.

Monotherapy analysis set

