3 PRIMARY AND SECONDARY VARIABLES

3.1 Derivation of RECIST Visit Responses

For all patients, the RECIST tumour response data will be used to determine each patient's visit response according to RECIST version 1.1. It will also be used to determine if and when a patient has progressed in accordance with RECIST and their best objective response to study treatment.

Baseline radiological tumour assessments are to be performed no more than 28 days before the start of randomised treatment and ideally as close as possible to the start of study treatment.

For patients who cross-over to savolitinib plus osimertinib based on confirmed objective disease progression during the initial randomised treatment period (including patients who have already crossed over based on confirmed PD prior to CSP V3.0) the baseline scan for response endpoints during the cross-over period will be the progression scan on savolitinib plus placebo, which should be acquired within 28 days of the start of treatment in the cross-over period. Scheduled RECIST 1.1 tumour assessments are not required for these patients, and the subsequent assessment of disease progression will be based on standard-of-care scan or investigator determined clinical progression.

For patients who cross-over after study unblinding and who have not objectively progressed during the initial randomised treatment period, scheduled RECIST 1.1 tumour assessments are

required using initial randomisation as baseline. Patients who then discontinue study intervention after cross-over for reasons other than investigator-confirmed disease progression will continue scheduled RECIST 1.1 tumour assessments until objective disease progression per RECIST 1.1 as assessed by investigator, unless they withdraw consent to the entire study. These tumour assessments are then performed every 6 weeks following the start of study treatment up to 24 weeks relative to initial randomisation, then every 8 weeks until objective disease progression.

If an unscheduled assessment is performed, and the patient has not progressed, every attempt should be made to perform the subsequent assessments at their scheduled visits. This schedule is to be followed in order to minimise any unintentional bias caused by some patients being assessed at a different frequency than other patients.

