3.2.2 Progression free survival (PFS)

PFS is defined as the time from randomisation until the date of objective disease progression or death (by any cause in the absence of progression) regardless of whether the patient withdraws from randomised therapy or receives another anti-cancer therapy prior to progression (i.e. date of PFS event or censoring – date of randomisation + 1). Patients who have not progressed or died at the time of analysis will be censored at the time of the latest date of assessment from their last evaluable RECIST assessment. However, if the patient progresses or dies immediately after two or more consecutive missed visits, the patient will be censored at the time of the latest evaluable RECIST 1.1 assessment prior to the two missed visits (Note: NE visit is not considered as missed visit).

Given the scheduled visit assessment scheme (i.e. six-weekly for the first 24 weeks then eight-weekly thereafter) the definition of 2 missed visits will change, as follows and summarised in [Table 6](#).

- If the previous RECIST assessment is less than study day 134 (i.e. week 19) then two missing visits will equate to 14 weeks since the previous RECIST assessment, allowing for early and late visits (i.e. $2 \times 6 \text{ weeks} + 1 \text{ week for an early assessment} + 1 \text{ week for a late assessment} = 14 \text{ weeks}$).
- If the two missed visits occur over the period when the scheduled frequency of RECIST assessments changes from six-weekly to eight-weekly this will equate to 16 weeks (i.e. $6 \text{ weeks} + 8 \text{ weeks} + 1 \text{ week for an early assessment} + 1 \text{ week for a late assessment} = 16 \text{ weeks}$). The time period for the previous RECIST assessment will be from study days 134 to 168 (i.e. week 20 to week 24).
- From week 25 onwards (when the scheduling changes to eight-weekly assessments), two missing visits will equate to 18 weeks (i.e. $2 \times 8 \text{ weeks} + 1 \text{ week for an early assessment} + 1 \text{ week for a late assessment} = 18 \text{ weeks}$).

Table 6 Definition of Two Missed Visits

Scheduled assessment	Previous assessment scan	Two missed visits window
Week 7	No evaluable scan or no screening scan	2 x 6 weeks + 2 weeks = 14 weeks (98 days) (relative to randomisation)
Week 7	Screening scan	2 x 6 weeks + 2 weeks = 14 weeks (98 days) (relative to randomisation)
Q6W up to Week 25	> Day 1 – Day 133 (up to Week 19)	2 x 6 weeks + 2 weeks = 14 weeks (98 days)

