4.2.5.2 Adverse events (AEs)

Adverse events will be coded using the most recent version of MedDRA that have been released for execution at AstraZeneca. Adverse events will be graded according to the National Cancer Institute CTCAE (Version 5.0).

Summary information (the number and percent of patients per treatment group) by system organ class and preferred term will be tabulated for savolitinib plus placebo and savolitinib plus osimertinib for:

- All AEs
- All AEs possibly related to study medication (as determined by the reporting investigator)
- AEs with maximum reported CTCAE grade
- AEs with CTCAE grade 3 or higher
- AEs with CTCAE grade 3 or higher, possibly related to study medication (as determined by the reporting investigator)
- Most common AEs (occurring in at least 10% of patients)
- Most common non-serious AEs (occurring in at least 5% of patients)
- AEs with outcome of death
- AEs with outcome of death possibly related to study medication (as determined by the reporting investigator)
- All SAEs
- All SAEs possibly related to study medication (as determined by the reporting investigator)

- AEs leading to discontinuation of study medication
- AEs leading to discontinuation of study medication, possibly related to study medication (as determined by the reporting investigator)
- AEs leading to dose reduction of study medication
- AEs leading to dose reduction of study medication, possibly related to study medication (as determined by the reporting investigator)
- AEs leading to dose interruption of study medication
- AEs leading to dose interruption of study medication, possibly related to study medication (as determined by the reporting investigator).

AEs with outcome of death, SAEs, AEs leading to discontinuation of each treatment and AEs possibly related to treatment will be listed.

Any AE occurring before the first dose of study intervention will be included in the data listings but will not be included in the summary tables of AEs. Adverse event summary tables will include only treatment-emergent AEs. The following events are considered treatment emergent:

- Adverse events with an onset date on or after the first dose of randomised study intervention and within the safety follow-up period (28 days [\pm 7 days] after last dose of all study intervention). Any events in this period that occur after a patient has received further therapy for cancer (following discontinuation of all study intervention) will be flagged in the data listings.

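### The SAP does not say whether cross-over before progression ends response assessment, so ORR, BoR and best tumour change for savolitinib plus placebo can include effects of the combination

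*SAP*

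**What the plan says.** SAP section 1.2 states that, after the initial data cut-off has been cleaned and the study unblinded, "patients on savolitinib monotherapy (savolitinib plus placebo) will be given the opportunity to cross-over to the savolitinib plus osimertinib arm". Progression is not a condition. Section 3.1 has a separate rule that begins "For patients who cross-over after study unblinding and who have not objectively progressed during the initial randomised treatment period"; for these patients scheduled RECIST assessments are "required using initial randomisation as baseline". The same section goes on to "Patients who then discontinue study intervention after cross-over for reasons other than investigator-confirmed disease progression", so it counts the cross-over regimen as study intervention.

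Efficacy is analysed as randomised. Section 2.1: "The FAS will include all randomised patients with treatment groups assigned in accordance with the randomisation, regardless of the treatment actually received".

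The response endpoints then use these data windows:

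- **ORR (3.2.1):** "Data obtained up until progression, or last evaluable assessment in the absence of progression, will be included in the assessment of ORR". The one exclusion is a response in a patient who stopped randomised treatment without progression, was given a subsequent anti-cancer therapy, and only then responded.
- **BoR (3.2.5)** and **best change in tumour size (3.2.6):** assessments stop at progression or at the start of subsequent cancer therapy.
- **PFS (3.2.2):** time runs "regardless of whether the patient withdraws from randomised therapy or receives another anti-cancer therapy prior to progression".
- **DoR (3.2.3):** the end date is the PFS date.

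None of these sections says whether cross-over is a subsequent anti-cancer therapy.

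**The concern.** The primary objective sets the ORR of the combination against that of savolitinib plus placebo, so the monotherapy figure should describe savolitinib without osimertinib. A patient who has neither progressed nor responded at unblinding may add osimertinib, be scanned against the original baseline, and show a first response on the combination. If the exclusion does not apply, that patient is a responder in the savolitinib plus placebo arm. Only that arm can cross over, so nothing offsets this in the other arm.

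Two programmers could read the rule differently and produce different primary-endpoint results. The SAP leaves that choice to be made after treatment codes are known.

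**Working it through.** The SAP states no figure that bears on this point, so there is none to reproduce. The check is a trace of the rules, followed by illustrative arithmetic.

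**Step 1. Do the scans exist?** Yes. Section 3.1 requires scheduled scans on the randomisation baseline for patients who switch without progression. The final data cut-off comes 9 months after the last randomisation (4.2.4).

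**Step 2. Are they in the ORR window?** Yes, unless the exclusion applies. The window closes at progression or at the last evaluable assessment.

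**Step 3. Does the exclusion apply?** The text does not settle it.

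- Against: section 3.1 calls the cross-over regimen study intervention. Section 4.2.5.2, on adverse events, places further cancer therapy "following discontinuation of all study intervention". A patient who switches also stays on savolitinib, so has not plainly stopped randomised treatment.
- For: section 3.1 separates the initial randomised treatment period from what follows, so moving to open-label osimertinib can be read as leaving randomised treatment for a new therapy.

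**Step 4. Is cross-over handled elsewhere?** Yes. Section 4.2.5.1 splits adverse events in the placebo arm at cross-over, and section 3.2.6 has a week-12 rule for patients who progress and then cross over. Response after cross-over without progression has no matching rule.

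**Step 5. Who can change the result?** For investigator ORR, only placebo-arm patients with neither progression nor response at the switch who respond later. Patients who cross over after investigator-assessed progression cannot, because the window has closed. BICR may reach further. It reads all scans of all patients, including unscheduled ones (3.1.4), so a patient with investigator progression but no BICR progression could have later scans counted.

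**Step 6. Direction.** A longer window can add a responder but cannot remove one, and a best response over a longer window cannot become worse. So ORR and BoR for this arm can only stay the same or rise.

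**Step 7. Size.** Each added response moves ORR by 100/n points, where n is the number with measurable disease at baseline:

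- 100/28 = 3.6
- 100/20 = 5.0
- 100/15 = 6.7
- 100/10 = 10.0

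The 28 is the planned arm size, which will not be reached (1.3). Ten is the size of the Monotherapy analysis set (2.1), if all ten have measurable disease. Fifteen and 20 are assumptions, as is a rate before cross-over of about 20%.

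The intervals use the SAP's Clopper-Pearson method: for x responders of n, the lower limit is the 2.5% quantile of Beta(x, n−x+1) and the upper limit is the 97.5% quantile of Beta(x+1, n−x).

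| n | No response after cross-over counted | One counted | Two counted |
|---|---|---|---|
| 10 | 2/10 = 20.0% (2.5–55.6) | 3/10 = 30.0% (6.7–65.2) | 4/10 = 40.0% (12.2–73.8) |
| 15 | 3/15 = 20.0% (4.3–48.1) | 4/15 = 26.7% (7.8–55.1) | 5/15 = 33.3% (11.8–61.6) |
| 20 | 4/20 = 20.0% (5.7–43.7) | 5/20 = 25.0% (8.7–49.1) | 6/20 = 30.0% (11.9–54.3) |
| 28 | 6/28 = 21.4% (8.3–41.0) | 7/28 = 25.0% (10.7–44.9) | 8/28 = 28.6% (13.2–48.7) |

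**The case against.** The strongest reply is that the cut already exists. ORR excludes responses after a subsequent therapy, BoR and best change stop when one starts, and open-label osimertinib given after randomised treatment can be called one. The adverse-event wording in 4.2.5.2 defines nothing for efficacy. This stands in part. A reader might infer that the exclusion certainly misses cross-over, and the documents do not support that; they support only that the text leans that way and leaves the matter open. An open rule on the primary endpoint still needs closing.

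A reader might also infer that PFS is wrongly defined. It is not. Section 3.2.2 openly follows patients through treatment changes, which agrees with the intention-to-treat analysis set. An analysis censored at cross-over would be a supplement, with a risk of informative censoring because switching is elective.

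Nor does the upward direction extend to every endpoint. For PFS it would require that the combination delays progression, and the SAP gives no effect size. DoR could move either way, since a response first seen after cross-over enters late and has little follow-up.

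Finally, the planned primary analysis will not be performed (1.2). ORR is reported by arm without a difference or test (4.2.2.1), and comparative analysis is confined to PFS and OS with at least 20 events (section 6). So no planned between-arm ORR estimate is biased. That limits the consequence but does not remove it: the monotherapy ORR and its interval are still reported, and readers will set them beside the other arm.

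**Conclusion.** The point holds for ORR, BoR and best change in tumour size. As written, the SAP allows a first response or best shrinkage after cross-over without progression to be credited to savolitinib plus placebo. For ORR and BoR the effect can only favour that arm, by 100/n percentage points of ORR per such response: 3.6 at n = 28 and 10 at n = 10. The number of such patients and the final arm size are not given, so the total effect is unknown and may be nil. The table shows what one or two such responses would do, not what will happen.

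The point does not extend to a flaw in the PFS definition or to a known direction of bias in DoR.

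**What to change.** In sections 3.2.1, 3.2.5 and 3.2.6, state that for patients randomised to savolitinib plus placebo the first cross-over dose of osimertinib counts as the start of subsequent anti-cancer therapy, so later assessments are not used for ORR, BoR or best change. Say that this applies to investigator and BICR data and to the Monotherapy analysis set.

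For DoR, include only responders under that rule and leave the end date tied to PFS as in 3.2.3. Cutting DoR at cross-over while PFS runs on would break that tie.

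Keep PFS as defined in 3.2.2. Optionally, add in 4.2.3.1 a supplementary PFS, with a matching DoR, censored at the last evaluable scan before the first cross-over dose, and apply the same 20-event condition to its hazard ratio.

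The cost is a few lines of SAP text, one date cut in the response data and, if the supplement is wanted, one further PFS table with its DoR counterpart. The supplement will have fewer events and may be subject to informative censoring, which should be stated beside it. No patient's treatment or assessment schedule changes.
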